scan, induced activation in areas that usually correspond to arousal, attention and cognitive control while in participants where smoking was not allowed after the brain scan, such activation was non-existent in response to smoking cues²⁶. It is therefore important that craving induced cues are present; however most studies use such cues prior to the task or treatment. Further, there is no systematic study comparing a condition of rTMS without an external craving cue, versus a condition of rTMS in combination with a smoking craving cue at the time of treatment. So, it would be interesting to investigate whether craving induced cues during rTMS treatment could produce similar results to studies that used a smoking craving cue prior to treatment, comparing it with rTMS at rest, without a smoking craving cue, where treatment will not be dependent to the smoking cue. Finally, across studies on smoking cessation, it has been reported that researchers have used breath carbon monoxide (CO) cut-off values ranging from 4 to 10 ppm to define abstinence in cigarette-smoking cessation. It has been furtherly demonstrated by Murray Jarvik³⁴ that there is a negative correlation between blood nicotine levels and craving for cigarettes while carbon monoxide has shown to correlate significantly with nicotine blood levels.

On the bases of previous research findings, in this study, we are going to compare tobacco cravings between three groups (two experimental and one control) of tobacco smokers that wish to quit smoking, after a five-day treatment of five 3-minute theta burst repetitive transcranial magnetic stimulation which will be applied over the left DLPFC. We hypothesize that:

- (A) The two experimental groups (group A that will receive real rTMS, four sessions per day of intermittent theta burst, for three minutes per session, for five consecutive days, while watching a smoking video as a cue for craving, and group B group that will receive real rTMS, four sessions per day of intermittent theta burst, for three minutes per session, for five consecutive days, with no presentation of the smoking video as a cue for craving, but presentation of a neutral video) will present lower craving scores in relation to their baseline measures,

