- (B) The two experimental groups, (groups A and B) will present lower craving scores in relation to the placebo group (group C will receive sham rTMS four sessions per day of intermittent theta burst, for three minutes per session, for five consecutive days, while watching a smoking video as a cue for craving) after the end of rTMS treatment,
- (C) We investigate the difference between the presentation or absence of visual cue among the two experimental groups (group A and B that will both receive real rTMS, with the difference that group B will not be presented a smoking video as cue for craving) as to whether presentation or absence of stimuli influences outcome of craving scores.

Method

Participants

Recruitment of participants will be done through public advertisements of the study, as participants belong in the healthy population. Individuals who agree to participate in this study will be volunteers. The minimum number of participants required was determined by an a priori power analysis where at least a sample size of 100 participants was suggested. (*Measures that suggested this sample size were determined by the mixed model, a small to medium effect size (0.4), at an alpha level of probability of 0.05).

Inclusion criteria of participants will be: (a) to be native speakers of the Greek language, (b) to be over the age of 18, (c) to be tobacco dependent users that wish to quit smoking.

Exclusion criteria of participants will be: (a) individuals with metallic parts inside or near the skull, (b) dependency of any other substances apart from nicotine and caffeine.

For the purposes of this study, participants will be formed into three groups. The groups will be as described below:

(A) An experimental group of 34 participants that satisfy all criteria for inclusion. This group will receive real rTMS, four sessions per day of intermittent theta burst, for three minutes per session, for five consecutive days, while watching a smoking video as a cue for craving;

(B) An experimental group of 34 participants that satisfy all criteria for inclusion. This group will receive real rTMS, four sessions per day of intermittent theta burst, for three minutes per session, for five consecutive days, with no presentation of the smoking video as a cue for craving, but a neutral video;

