These questionnaires will be administered to each participant prior to the first day of TMS treatment, after the last day of TMS treatment, after one week, after one month, and after six months. Participants will complete the questionnaires on a 14" laptop at baseline and first follow up, and then online during the remaining follow ups. The aim of the questionnaires will be to test for nicotine dependence, levels of craving, and screening for anxiety levels of participants at different time points. Those data will then be used for within and between participants' analyses. Further, participants will be asked through a visual analogue scale ranked from 1-100 "How much do you want to smoke right now?", prior and after each TMS session, as previously used by Revital Amiaz in similar methodology studies, to assess cue-induced craving of participants.

Smokerlyzer

Smokerlyzer is a non-invasive tool that measures the amount of CO on a smoker's breath and establishes smoking status biochemically. It will be used prior to each TMS session every day for each participant and its measures will be later used for analyses purposes.

Craving Videos

Two videos will be used during the TMS sessions, presented in a randomized manner. The first video is a smoking video which lasts for three minutes and its purpose is to be a cue for inducing craving. The other video used will be a neutral video, illustrating daily tasks that do not involve smoking. This video will be used as a control video.

TMS Protocol

This study will attempt to use accelerated theta burst stimulation of TMS, and specifically the 3-minute FDA-approved protocol for depression. rTMS will be applied to each participant for a period of five consecutive days. Each day will consist of four sessions of the 3-minute theta-burst stimulation with a 45-minute gap (which is the optimal gap) between sessions. The protocol includes 2 seconds of stimulation on the left dorsolateral prefrontal cortex which is followed by an 8 second pause. There will be 600 pulses in total for each 3-minute session. The site of stimulation will be the left DLPFC. It will be measured by using the 10-20 system, it will be determined by the Beam F3 software and it will be at 100% of the motor threshold.

Planned Analysis

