The data will be analysed in SPSS. Analyses of hypotheses will be carried out with a mixed model (repeated measures within and between factors). Within factors will be determined from the craving scores in the baseline and follow ups from the three questionnaires, and CO measures. Between factors will be determined by the three experimental groups. Analyses will be adjusted for sex, age and visual stimuli.

Expected outcomes & Benefits of the study

Few studies have examined smoking cessation through a TMS treatment. Further, there is a question as to whether exposure to behavioural cues before or during TMS treatment may influence craving outcomes, which may improve our understanding in the mechanisms that influence successful outcome, while using induced plasticity methods. While we expect that experimental groups will have significantly decreased craving scores compared to control group, generally this study will aid in our understanding regarding potential options for smoking cessation and possibly for other addictions with similar physiological mechanisms.

References

1. World Health Organization. (2015). WHO global report on trends in tobacco smoking 2000-2025. Geneva: WHO.
2. US Department of Health and Human Services. (2014). The health consequences of smoking—50 years of progress: a report of the Surgeon General. Atlanta, GA: US Department of Health and Human Services, Centers for Disease Control and Prevention, National Center for Chronic Disease Prevention and Health Promotion, Office on Smoking and Health, 17.
3. US Department of Health and Human Services. (2010). How tobacco smoke causes disease: What it means to you. Atlanta: US Department of Health and Human Services, Centers for Disease Control and Prevention. National Center for Chronic Disease Prevention and Health Promotion, Office on Smoking and Health.
4. European Commission (2015). Retrieved from: <https://goo.gl/1qkJFx>
5. Brody, A. L., & Cook, I. A. (2011). Manipulation of cigarette craving with transcranial magnetic stimulation. *Biological psychiatry*, 70(8), 702.
6. Goldstein, M. G., Niaura, R., Willey, C., Kazura, A., Rakowski, W., DePue, J., & Park, E. (2003). An academic detailing intervention to disseminate physician-delivered smoking cessation counseling: smoking cessation outcomes of the Physicians Counseling Smokers Project. *Preventive medicine*, 36(2), 185-196.

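### Baseline craving enters the model as a repeated level and not as a covariate, which costs power for hypotheses B and C; hypothesis A is an uncontrolled before-after test

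*Combined protocol and SAP*

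**What the plan says.** The Planned Analysis is a short paragraph. It specifies a mixed model in SPSS with within-participant and between-participant factors, the latter being the three groups. On the within side it states: "Within factors will be determined from the craving scores in the baseline and follow ups from the three questionnaires, and CO measures". On covariates it states: "Analyses will be adjusted for sex, age and visual stimuli". It gives no covariance structure, no constraint on baseline means and no contrast for any hypothesis.

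The hypotheses are at the end of the Introduction. Hypothesis A is that the two active groups "will present lower craving scores in relation to their baseline measures". Hypothesis B is that they "will present lower craving scores in relation to the placebo group" once treatment has ended. Hypothesis C is worded "We investigate the difference between the presentation or absence of visual cue among the two experimental groups", with no time point.

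Under Materials, the questionnaires are "administered to each participant prior to the first day of TMS treatment" and then at four later times: end of treatment, one week, one month and six months. The Participants section plans 34 per group and bases the sample size on "a small to medium effect size (0.4), at an alpha level of probability of 0.05".

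**The concern.** In a randomised comparison of a continuous score, the pre-treatment value of that score is usually the most useful covariate available. Treating it as one more repeated level does not by itself give that benefit. If baseline means may differ between groups, the model offers two end-of-treatment comparisons of two groups: the difference in change from baseline, or the difference at that visit alone. Change carries the full noise of the baseline measurement; the visit contrast ignores baseline. The plan does not say which it will use. With 34 per group the lost precision matters most for modest effects, including the cue comparison of A with B, where both arms receive real stimulation.

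Hypothesis A is a different problem. Participants are volunteers who wish to quit, so craving may fall in every arm, sham included. A before-after test in the active arms counts that shared fall in its favour. It can succeed when rTMS adds nothing to sham.

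**Working it through.** **1. The plan's own figure.** Participants gives an effect size of 0.4, alpha 0.05 and at least 100 participants, but no power and no metric for 0.4. Read as Cohen's f in a one-way three-group ANOVA, the noncentrality is N·f² = 100 × 0.16 = 16 on 2 and 97 df, and power is 95.1% (95.5% at 102). At 80% or 90% power the same test needs 64 or 83. So 100 is reproduced only with an assumed 95% power and a single-time-point test that uses no baseline information. What follows does not depend on this reading.

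**2. Variances.** Let the craving score have SD 1 at baseline and follow-up, with correlation ρ between them. Per-participant variance behind a two-group contrast at one visit:

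- unadjusted: 1
- change from baseline: 2(1 − ρ)
- baseline as covariate: 1 − ρ²

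For 0 < ρ < 1 the last is the smallest. The ratio of change to adjusted is 2/(1 + ρ); the ratio of unadjusted to adjusted is 1/(1 − ρ²).

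| | ρ = 0.3 | ρ = 0.5 | ρ = 0.7 |
|---|---|---|---|
| Change variance | 1.40 | 1.00 | 0.60 |
| Adjusted variance | 0.91 | 0.75 | 0.51 |
| Change / adjusted | 1.54 | 1.33 | 1.18 |
| Unadjusted / adjusted | 1.10 | 1.33 | 1.96 |

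The ratios are also sample-size multipliers.

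**3. Power, 34 v 34, two-sided 0.05.** Noncentral t with 66 df (65 with the covariate) and noncentrality d/√(variance × 2/34). For example, with d = 0.5 and ρ = 0.5: change or unadjusted 0.5/√(1 × 0.0588) = 2.06, power 53%; adjusted 0.5/√(0.75 × 0.0588) = 2.38, power 65%. The document gives neither ρ nor the SD, so d and ρ are assumptions.

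| Assumed difference | Analysis | ρ = 0.3 | ρ = 0.5 | ρ = 0.7 |
|---|---|---|---|---|
| 0.4 SD | Change | 28% | 37% | 56% |
| | Unadjusted | 37% | 37% | 37% |
| | Adjusted | 40% | 47% | 62% |
| 0.5 SD | Change | 40% | 53% | 75% |
| | Unadjusted | 53% | 53% | 53% |
| | Adjusted | 57% | 65% | 81% |
| 0.85 SD (f = 0.4) | Change | 83% | 93% | 99% |
| | Unadjusted | 93% | 93% | 93% |
| | Adjusted | 95% | 98% | 99.8% |

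The last block takes 0.4 as Cohen's f with A and B equal and sham different by δ. Then f = δ√(2/9), so δ = 0.4/0.471 = 0.85 SD. A three-arm simulation of 6,000 runs at 0.5 SD gave the same powers to the nearest percent.

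The difference detectable with 80% power at ρ = 0.3, 0.5 and 0.7 is 0.82, 0.69 and 0.53 SD (change), 0.69 SD (unadjusted), and 0.66, 0.60 and 0.49 SD (adjusted).

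**4. Group main effect over all five levels.** If this term were the test, the pre-treatment level, where no effect is possible, would shrink a sustained effect to 4/5. The plan does not say that this is the test.

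**5. Hypothesis A.** Assume every arm falls 0.3 SD, ρ = 0.5 and no rTMS effect. The change score then has SD √(2 × 0.5) = 1. The paired t noncentrality is 0.3 × √34 = 1.75 in one active arm, giving a significant fall with probability 40%. Pooling both active arms, it is 0.3 × √68 = 2.47, giving 68%. A simulation of 20,000 runs gave 39% and 68%, while the baseline-adjusted A versus C contrast rejected 5% of the time.

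**The case against.** The strongest reply is that nothing here is invalid. Groups are randomised, so change and post-treatment contrasts are both unbiased with correct type I error. Baseline among the outcomes is also the starting point for a model with equal baseline means, which would recover almost all the efficiency, and the plan does not exclude it. This stands as a limit on the claim: the fault is lost precision through a choice not made. The plan does not adopt that constraint either, and its covariate list omits baseline craving.

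The size rests on assumed inputs. The 0.5 SD is not in the document, and on the Cohen's f reading hypothesis B loses only about 5 points at ρ = 0.5 (93% against 98%). That is fair, although the f reading needs an unstated 95% power, sits awkwardly with the plan's description of 0.4 as small to medium, and says nothing about A versus B.

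Equal SDs at baseline and follow-up are also assumed. With baseline SD 0.8 of the follow-up SD, the change variance is 1 + 0.64 − 1.6ρ, and its ratio to adjusted falls to 0.84/0.75 = 1.12 at ρ = 0.5 and 0.52/0.51 = 1.02 at ρ = 0.7. With s the ratio of baseline to follow-up SD, the change variance equals (s − ρ)² + 1 − ρ². It is therefore never below the adjusted variance, but can come close to it.

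Hypothesis B could be read as pooled active against sham, 68 v 34. At 0.5 SD and ρ = 0.5 that gives 66% for change or unadjusted and 78% adjusted: higher power, same gap.

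Finally, hypothesis A is true as worded if scores fall in all arms, so the 40% and 68% are not false positives for A itself, and hypothesis B supplies the sham comparison. That is correct. The point about A is confined to what it can support.

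**Conclusion.** The concern holds. As written, the comparisons for hypotheses B and C are change or unadjusted contrasts, and a baseline-adjusted analysis is more precise than either for any correlation strictly between 0 and 1 when the SDs are equal. Unequal SDs change the size of the loss and never make change the more precise choice. At 0.5 SD, the gain in power from adjustment is 6 to 17 points over change and 4 to 28 points over the unadjusted contrast across ρ = 0.3 to 0.7. If the effect against sham is as large as f = 0.4 implies, the gain is at most about 12 points (83% to 95%, change, ρ = 0.3). These sizes depend on an assumed ρ, effect and SD ratio. The change should be made because it improves precision at no cost; the existing plan would not give biased group comparisons.

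Hypothesis A cannot by itself support an efficacy statement, because it does not separate rTMS from a fall shared with sham.

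**What to change.** In the Planned Analysis:

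- Fit a likelihood-based mixed model (SPSS MIXED, unstructured covariance) to the four post-treatment craving scores, with group, visit, group × visit, baseline craving, baseline × visit, sex and age. Keeping baseline as an outcome with its mean constrained equal across groups is an acceptable equivalent.
- Name the tests: A versus C and B versus C for hypothesis B, and A versus B for hypothesis C, each at end of treatment from this model. Hypothesis C has no stated time point, so one must be written in.
- Omit visual stimuli as a separate covariate if it only records the assigned video. Group already determines it (smoking video in A and C, neutral video in B).
- Report within-group change (hypothesis A) descriptively, and rest any efficacy statement on the contrasts with sham.

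The cost is wording. Baseline craving is already collected before the first treatment day, so no visit, measurement or participant is added.

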The researcher will then take the appropriate head measures using the 10-20 system and then will place a cap on the participant's head. The participant will sit on the TMS chair and the researcher will place the (real/sham) TMS coil on the participant's left DLPFC and start the session. While participants will be receiving TMS, they will be presented with a smoking video as a cue for craving, throughout each TMS session (except for one group that they will not be presented with a cue craving video, but with a neutral video). There are two available videos, and those will be presented in a randomised manner for each participant. After each session, participants will have a forty-five minute break and then return for the next TMS session. Once done with all five days of TMS therapy, they will be again assessed with the three questionnaires.

To protect personal data and for conditions to be double-blind (participants will not know whether they receive real or sham TMS and researcher will not know whether they administer real or sham TMS), participants will be pseudo-anonymised on an excel database and will be assigned in a randomised manner to each defined group. Demographic and personal data of participants will be confidential only to the researchers involved in the study and will be protected and handled according to the Data Protection Act 2018 and the ICH Good Clinical Practice for data protection. Recorded data of participants will include: demographic details, data of self-report questionnaires at baseline and follow up measures, and CO breath levels.

Following TMS treatment

Following the end of the rTMS treatment, participants will be contacted again to complete the three questionnaires. This will be done at one week, one month and six months post-TMS treatment.

Materials

Questionnaires

The tools used in this study are three questionnaires:

- The Fagerstrom Test of Nicotine Dependence (in Greek),
- The Factor Structure of Tobacco Craving-Short Form (will be adjusted to Greek),
- The Perceived Stress Scale (in Greek).

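### The model for hypotheses A–C draws craving scores from three questionnaires plus CO, but only one questionnaire measures craving, so the outcome that tests A–C is not defined

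*Combined protocol and SAP*

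**What the plan says.** The three hypotheses, at the end of the Introduction, are each stated in craving scores: against baseline (A), against sham (B), and with versus without the smoking cue (C). No other outcome appears in them.

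Materials, Questionnaires, lists three instruments: the Fagerstrom test of nicotine dependence, a short-form tobacco craving questionnaire and the Perceived Stress Scale. Their joint aim is "to test for nicotine dependence, levels of craving, and screening for anxiety levels of participants at different time points", so there are three aims for three instruments. Of the resulting data as a whole the same section says: "Those data will then be used for within and between" participants' analyses. It gives no instrument a separate role. It also describes a 1–100 visual analogue scale (VAS) of the wish to smoke, taken before and after each TMS session to capture cue-induced craving.

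Planned Analysis is one short paragraph. It assigns the hypotheses to a repeated-measures mixed model and describes the repeated part thus: "Within factors will be determined from the craving scores in the baseline and follow ups from the three questionnaires, and CO measures". The between factor is the three groups. The paragraph names no primary outcome and does not say whether the measures are modelled together or separately. It does not mention the VAS.

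**The concern.** Two of the three questionnaires do not yield a craving score, so craving scores from three questionnaires cannot be obtained as the sentence describes. Whoever runs the analysis has to choose: use the craving form alone, run one model per measure, or combine the measures in some way. The choices answer different questions, and nothing in the plan prevents the choice being made after the data are seen.

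At stake is what a positive result would mean. A fall in dependence, stress or CO could be reported as support for a hypothesis about craving, or a craving result could be blended with scales that carry no hypothesis.

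**Working it through.** The point rests on the text and on no figure in the plan, so there is no stated figure to reproduce.

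**Step 1: set each measure against the hypotheses.**

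| Measure | Construct given in the protocol | Schedule | In Planned Analysis? | Craving measure? |
|---|---|---|---|---|
| Fagerstrom test | nicotine dependence | baseline, end of treatment, 1 week, 1 month, 6 months | yes | no |
| Tobacco craving short form | craving | same five points | yes | yes |
| Perceived Stress Scale | stress (the stated aim says anxiety) | same five points | yes | no |
| Breath CO | smoking status | before each TMS session | yes | no |
| VAS | cue-induced craving | before and after each TMS session | no | yes |

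Four measures are named for the model that tests A–C, and one of them is a craving measure. The other craving measure collected, the VAS, is left out.

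**Step 2: compare the schedules.** The questionnaires have 5 time points. CO has 4 sessions × 5 days = 20 readings, all during the treatment week, and none is stated at 1 week, 1 month or 6 months. CO therefore cannot share the questionnaires' baseline and follow-up structure.

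**Step 3: consequence if each measure is tested separately.** Inputs: alpha 0.05, from Participants; k measures. Assumptions: one test per measure per hypothesis, independent tests, and any significant result counted as support.

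Chance of at least one false positive = 1 − (1 − 0.05)^k

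- k = 1: 1 − 0.95 = 0.050
- k = 3 (three questionnaires): 1 − 0.95³ = 1 − 0.8574 = 0.143
- k = 4 (with CO): 1 − 0.95⁴ = 1 − 0.8145 = 0.185

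Positive correlation between the measures lowers the last two figures towards 0.05.

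**Step 4: consequence if the scales are combined.** The plan describes no composite, so this is only a check on whether an effect could be sized. Take an equal-weight mean of three standardised scores with common correlation r. Suppose m of the three shift by d:

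composite effect = (m·d/3) / √((1 + 2r)/3)

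For illustration take d = 0.40 SD; the protocol gives an effect size of 0.4 without saying in what metric. With r = 0.2 the denominator is √(1.4/3) = 0.683; with r = 0.7 it is √(2.4/3) = 0.894.

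| Scales that shift | r = 0.2 | r = 0.7 |
|---|---|---|
| craving only (m = 1) | 0.133/0.683 = 0.195 | 0.133/0.894 = 0.149 |
| two scales (m = 2) | 0.267/0.683 = 0.390 | 0.267/0.894 = 0.298 |
| all three (m = 3) | 0.400/0.683 = 0.586 | 0.400/0.894 = 0.447 |

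The result runs from well below 0.40 to above it. The documents give neither the correlations nor the expected effects on dependence and stress, so even the direction of the change is open.

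**The case against.** The strongest reply is that this is loose drafting. The hypotheses and the expected-outcomes section speak only of craving, and Planned Analysis itself says craving scores. A fair reader could take it that the craving form tests A–C and that each other measure gets its own repeated-measures model. Saying that the data serve within- and between-participant analyses is not saying that the scales are pooled. This stands. A reader might infer that dependence and stress scores necessarily enter the test of every hypothesis, but the text does not settle that.

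Two other strong inferences also fail. One is that the model reverses roles by using scores as predictors. The reference to baseline and follow-ups makes time the evident within factor; the sentence is clumsy and no more. The other is that craving effects will be diluted and power lost by a calculable amount. No section proposes standardising, averaging or a composite, and an effect confined to craving is itself doubtful: the Introduction cites a trial of ten daily sessions in which active stimulation reduced nicotine dependence as well as consumption.

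The reply does not remove the conflict between the two sections. The benign reading is available but is stated nowhere, and followed literally the sentence is wrong.

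**Conclusion.** The concern holds in a limited form. Planned Analysis treats three questionnaires as sources of craving scores and adds CO, while Materials gives only one questionnaire a craving purpose. The plan therefore does not define the outcome for A–C, and it permits dependence, stress or CO to be mixed with craving or to stand in for it.

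If the measures are tested separately, the false-positive chance per hypothesis rises from 5% to at most about 14% (three questionnaires) or 19% (with CO), under the independence and any-positive-counts assumptions above. If they are combined, the loss is one of interpretation, and no dilution figure can be defended from the documents. If only the craving form is used, there is no harm, but the plan has to say so. This should be corrected before the data are analysed.

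The use of anxiety as a label for what the Perceived Stress Scale measures is an editorial slip. No hypothesis depends on it.

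**What to change.** Rewrite the model description in Planned Analysis as follows:

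- The within factor is time (baseline, end of treatment, 1 week, 1 month, 6 months) and the between factor is group.
- The outcome for A, B and C is the tobacco craving short-form score.
- The Fagerstrom score and the Perceived Stress Scale are secondary outcomes, each in its own model.
- CO is a secondary outcome in a separate model on its own schedule, before TMS sessions.
- The VAS is a secondary measure of cue-induced craving.

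Editorial only: in Materials, Questionnaires, replace anxiety with perceived stress.

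The cost is a change of analysis wording, with no new data or visits. The price to the investigators is that dependence, stress and CO results can no longer be claimed as support for A–C.

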(C) A control group of 34 participants that satisfy all criteria for inclusion. This group will receive sham rTMS four sessions per day of intermittent theta burst, for three minutes per session, for five consecutive days, while watching a smoking video as a cue for craving.

Design

This is a randomized, double-blind, sham-controlled study.

Procedure

Prior to the study

After advertisement of the study, potential participants will be able to contact the researcher via contact details that will be given on the advertisement. The researcher will then perform a screening interview (either by phone or email correspondence) regarding the eligibility of participants. The questions will include demographics and contact details: a) telephone number, b) email address, c) sex, d) education and occupation, e) age; and the screening will involve questions regarding eligibility: f) “how many cigarettes do you smoke per day?”, g) “for how long have you been a smoker?”, h) “has there been any period in your life that you managed to quit smoking; if yes for how long and how did you manage to do it?”, i) “are you dependant on any other substances e.g. alcohol/drugs/benzodiazepines apart from caffeine and nicotine”. These questions will be asked in Greek. If individuals meet the criteria and wish to continue, the researcher will arrange with participants details regarding their visit to the site.

At the research site

Participants will arrive at the Cyprus rTMS Centre, will receive all the required information about their participation, and if agreed, they will sign the consent form and will be led to the testing room. Participants will then complete three questionnaires on a PC, prior to the beginning of the experiment. The questionnaires are all described in Materials section and they are attached in the Appendix. All participants will undergo a breath carbon monoxide (CO) measure prior to each TMS session of each day with the use of a smokerlyzer. Further information about its use is described in the section below.

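### No primary outcome, visit or contrast is named and no error control is set, so the 0.05 level would not hold for the trial's conclusion: about 12% for three unadjusted craving contrasts at a single visit, more if repeated.

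*Combined protocol and SAP*

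**What the plan says.** Planned Analysis specifies a repeated-measures mixed model in SPSS. The between factor is the three groups, and the within factors are taken from "craving scores in the baseline and follow ups from the three questionnaires, and CO measures". The section is silent on primary outcome, visit, contrast, testing order, adjustment and test-level alpha.

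The hypotheses stand at the end of the Introduction, and all concern craving. Hypothesis A is a change from baseline within groups A and B. Hypothesis B is that both real-stimulation groups "will present lower craving scores in relation to the placebo group" once treatment has ended. Hypothesis C compares A with B.

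Under Materials (Questionnaires) there are three questionnaires, for dependence, craving and stress, given at baseline and after the last treatment day. For the later contacts, Procedure (Following TMS treatment) says: "This will be done at one week, one month and six months post-TMS treatment". That makes four post-baseline assessments. The same Materials section adds a 1–100 visual analogue scale (VAS) for craving before and after every session. Under Smokerlyzer, CO is taken before sessions on treatment days; none is planned at the later contacts.

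The only significance level is in Method (Participants), where the sample size was set "at an alpha level of probability of 0.05". Each group has 34 participants.

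**The concern.** The hypotheses point to craving but do not settle which test decides them.

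- **Instrument.** Both the craving short form and the VAS measure craving, and Planned Analysis loosely attributes craving scores to all three questionnaires.
- **Visit.** Hypothesis B's timing fits any of the four post-baseline assessments.
- **Contrast.** Hypothesis B covers two comparisons with sham and Hypothesis C adds a third. None is ranked.

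The section on expected outcomes anticipates a significant reduction against control, so a confirmatory claim is intended. Without a rule fixed in advance, the analyst can choose among several craving results after seeing the data, and a nominal p below 0.05 no longer carries a 5% false-positive risk.

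**Working it through.** The documents give no overall error rate to reproduce. Their one calculated figure, a minimum of 100 participants, has no stated power and does not bear on this point.

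**Inputs from the documents**
- Groups: 3, with 34 in each (Method, Participants), so 3 pairwise contrasts.
- Post-baseline questionnaire assessments: 4 (Materials, Questionnaires).
- Questionnaires: 3. CO is counted only in the last row of the table.
- Level: 0.05.

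**Assumptions, because the documents are silent**
- Two-sided tests.
- No true effect of any kind.
- Between-visit correlation 0.4–0.8 and between-scale correlation 0.2–0.6.
- Each contrast is approximated by a t-test on simulated normal data with 34 per group, ignoring covariates.

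**Formula.** For m independent tests, the chance of at least one false positive is 1 − 0.95^m. This is a reference value only, because contrasts that share a group, visits in one person and scales in one person are all correlated. The simulated column allows for that.

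| Reading of the plan | Tests m | 1 − 0.95^m | Simulated |
|---|---|---|---|
| One craving score, one visit | 3 | 14.3% | about 12% |
| One craving score, four visits | 3 × 4 = 12 | 46.0% | about 25–38% |
| Three questionnaires, four visits | 3 × 4 × 3 = 36 | 84.2% | about 52–73% |
| One overall group test on each of three questionnaires | 3 | 14.3% | about 9–14% |
| The same, with CO as a fourth outcome | 4 | 18.5% | about 9–18% |

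The last two rows use between-outcome correlations from 0 to 0.9. The first row needs no correlation assumption, since it uses one score at one visit. The table leaves out the VAS and the within-group tests of Hypothesis A, which would add tests.

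**Check of the remedy.** Holm compares the ordered p-values with 0.05/3 = 0.0167, 0.05/2 = 0.025 and 0.05. With no effect, any rejection requires the smallest p-value to be at or below 0.0167, so the chance is at most 3 × 0.0167 = 0.05, whatever the correlation between contrasts.

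**The case against.** The strongest reply is that the plan specifies a mixed model, not a grid of separate tests. Such a model handles the visits jointly. For one scale and exactly three groups, pairwise tests made only after a significant overall group test would hold about 5%. The hypotheses also confine confirmatory interest to craving, and Materials gives the other two questionnaires different purposes. A significant stress score beside a null craving score would support none of the stated hypotheses.

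Much of this stands, and it rules out a stronger reading that a reader might infer: that three contrasts, four outcomes and four visits give 3 × 4 × 4 = 48 tests at 0.05, so that the trial's error rate is well above one half. The documents do not support that, for four reasons.

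- No cell-by-cell testing and no test-level alpha is stated.
- CO is not scheduled at the three later contacts, so a full 48-cell grid does not exist.
- The hypotheses concern craving only.
- The correlations that drive the figure are not in the documents.

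The reply does not remove the core point. The plan does not say that pairwise tests are conditional on an overall test. An overall test alone cannot answer Hypotheses B and C, which name particular comparisons. Even a single craving score at a single visit leaves three unadjusted contrasts. The mixed model does not choose between the short form and the VAS, or among the visits.

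**Conclusion.** The concern holds in a limited form. The plan designates no primary outcome, visit or contrast and controls no error rate, and any reading with more than one unadjusted test exceeds 0.05. The firmest figure is about 12%, for the three contrasts that Hypotheses B and C require, on one craving score at one visit. About 25–38% applies if that score is tested at all four visits, given the assumed between-visit correlation. A figure above 50% belongs only to the case in which every questionnaire, visit and contrast is tested at 0.05. It is a possible use of the plan, not its stated rule, and should not be quoted as the trial's error rate. All figures assume no true effect and two-sided tests.

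**What to change.** In Planned Analysis, before any unblinded analysis:

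1. Name the total score of the tobacco craving short form at the end-of-treatment assessment as the single primary outcome.
2. Take the three between-group contrasts of Hypotheses B and C (A vs C, B vs C, A vs B) from the mixed model at that assessment, with Holm adjustment at two-sided 0.05 overall. A fixed testing order would also control the error, but it would make some of these contrasts depend on the success of others, although Hypothesis B names both real-stimulation groups. Holm needs no such ranking.
3. Treat Hypothesis A, the later visits, the dependence and stress scales, CO and the VAS as secondary. Report them as estimates with 95% confidence intervals and no confirmatory claim.

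Craving is proposed because all three hypotheses concern it. The Objectives also mention quitting success. If the sponsor prefers that or another visit as primary, the same rule applies, provided the choice is made in advance.

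The cost is one paragraph and no new data. Each contrast has slightly lower power than an unadjusted test, and the secondary measures and later visits, including six months, can no longer carry a confirmatory claim.
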